Newborn infants born at term normally lose 5-10% of their body weight in the first week of life due to contraction of extracellular water compartment.^{12,13} The proportion of weight loss is significantly higher in VLBW infants.¹² Increased insensible water loss is widely considered as the main cause for additional weight loss in this population.^{14,15} Nevertheless, studies identified low energy intake to be a key driver to excessive weight loss.^{13,16} In fact, an earlier study showed that significant postnatal weight loss occurs mainly in infants whose energy intake is inadequate.¹³ A more recent epidemiologic study demonstrated similar postnatal growth trajectories with minimal crossing of percentiles after the initial weight loss regardless of gestational age at birth.¹¹ The growth trajectories for infants in that study had similar slopes and growth rates which indicate that proportion of postnatal weight loss is a lead cause for EUGR at discharge.¹¹ Therefore, we speculate that decreasing the maximum percentage of initial weight loss in the acute stage would keep the preterm infant on a higher growth trajectory that is enough to reduce incidence of EUGR.

Current fat provision regimen for preterm infants include starting parenteral lipid at 12-24 hours of age with 0.5-1 g/kg per day and advancing by 0.5 g/kg/day until reaching 3 g/kg per day. Using early (within one hour of birth) and higher (start at 2 g/kg per day and advance to 3g/kg per day once total fluid intake is increased to 80 ml/kg/day) parenteral fat intake could reduce the cumulative caloric deficit in the acute stage. Because of high-density energy in fat, higher parenteral fat intake will reduce the early energy deficit and enhance protein accretion. The first 2-3 weeks of life offer a critical window to limit postnatal nutritional and energy deficits.⁵ Recent study showed that higher energy and fat intakes during the first 2 weeks after birth are associated with a lower incidence of brain lesions and dysmaturation at term equivalent age in preterm neonates.¹⁷

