To date, studies of “early aggressive nutrition” in preterm infants have mainly focused on high protein intake to prevent protein catabolism.¹⁸⁻²¹ Nevertheless, provision of high protein intake without enough energy is unlikely to significantly reduce the early loss of protein and fat mass that had been accreted before birth. Early and high protein intake is currently a standard of care in our neonatal intensive care unit (NICU).

In summary, provision of high and early fat intake may help reducing the amount of postnatal weight loss. It may also help utilize the high amount of protein that is currently recommended to these premature babies. Also, we expect babies who get this appropriate intake to regain their birth weight earlier than others on slow fat increase regimen.

Methodology

Hypothesis:

We hypothesize that early higher fat intake in the first week after birth in VLBW infants results in less weight loss compared to the traditional provision of intravenous fat.

Study Design:

This is a randomized, non-blinded, controlled trial that will take place from March 2018 through February 2020 at the 39-bed level III NICU at Foothills Medical Center, Calgary, Alberta.

Intervention:

Starting Intravenous Lipid emulsions from D0 at 2 g/kg/day in the experimental group and increase to 3 g/kg/day the next day.

Comparison:

Control group: traditional start by 0.5-1 g/kg/day on D0 and increase daily by 0.5 g/kg/day till reaching 3 g/kg/day.

Outcome:

- Primary: The maximum percentage of weight loss in the acute stage of nutritional support: Defined as (birth weight–lowest postnatal weight)/birth weight× 100).
- Secondary:
 - Time to regain birth weight (day).
 - Time to reach 90 Kcal/kg/day (day).
 - Lipid tolerance: using serum TG levels (intolerance will be defined as TG> 2.8 mmol/L).
 - Incidence of EUGR at 36 weeks and at discharge.
 - Growth anthropometrics (weight, length and HC Z scores at 36 weeks and at discharge).
 - Incidence of ROP, BPD (28 days, 36 weeks CGA), brain injury and NEC.
 - Survival free major morbidity (BPD, ROP, NEC and severe IVH) at discharge.
 - Incidence of severe neurodevelopmental outcome at 18-22 months corrected gestation.
 - Length of stay.
 - Death.

Study Population:

a) Inclusion Criteria:

1. Preterm infants born with birth weight < 1500 g at Foothills Medical Centre (FMC)
2. Appropriate for gestational age (AGA) as per Fenton's growth charts
3. Anticipated duration of PN for >7 days

b) Exclusion Criteria:

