1. Infants with congenital anomalies
2. Infants with suspected inborn errors of metabolism or family history of inborn error of metabolism
3. Infants with suspected or confirmed biliary atresia
4. Infants born small for gestational age (SGA)
5. Confirmed early sepsis

Twins and triplets who meet the weight and AGA status criteria will be randomized to the same arm of the study. Informed written consent will be obtained from a parent of each infant before birth or shortly after the infant's admission to the NICU and before starting parenteral lipid emulsions.

Time frame: March, 2018 to April, 2020

Study Protocol:

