The investigators will conduct the randomization using a computer-generated allocation sequence (in random sized blocks for allocation concealment and balanced groups) generated at the University of Calgary. The lipid emulsions will be administered through an umbilical venous catheter, peripherally inserted central catheter, or peripheral line. The control group will begin treatment with 0.5 g/kg per day of 20% Intravenous Lipid Emulsion (IVLE) after birth if the birth weight is less or equal 1000g or 1 g/kg per day if birth weight is more than 1000g. The experimental group will begin treatment with 2 g/kg per day of 20% IVLE after birth. The IVLE dose in the control group will be increased by 0.5 g/kg per day daily until reaching 3 g/kg per day. The dose of IVLE will be increased directly from 2 to 3 g/kg per day the next day in the experimental group. Other macronutrients and micronutrients will be provided using the same products for amino acid and dextrose solutions in both groups. The maximum intake of amino acid will be 4 g/kg per day. The initial dextrose concentration in the parenteral nutrition (PN) will be 12.5%. The glucose infusion rate will be calculated and will be adjusted at the discretion of the attending neonatologist depending on the blood sugar levels. Total fluid intake will be started at 60 mL/kg per day for all infants. Monitoring for serum triglyceride will be performed after 24h of each lipid increment as per NICU policy in VLBW infants. This is part of routine care and not additional investigation. The serum triglyceride (TG) levels and other biochemical measurements such as serum electrolytes and acid-base status will be analyzed by the Calgary laboratory services at FMC. If hypertriglyceridemia occurs (>2.8 mmol/L, as per our current protocol), the IVLE concentration will be adjusted according to the following approved algorithm (Table 1).

Triglyceride Level (mmol/L)	Action
< 2.8	
 • Advance lipid intake as planned
2.8 – 4.5	
 • Reduce to previously tolerated dose
Greater than 4.5	
 • Stop lipid infusion for 24 hours

Table 1: Algorithm for adjusting IVLE in TPN.

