Infants will be weighed every day on electronic scales with a precision of 2 grams by nursing personnel, using the In-Bed scale. Other anthropometric measurements such as length and head circumference will be taken by nursing personnel on admission and then weekly till discharge with a newborn length board and measuring tape respectively. Classification of newborns to define appropriate-for gestational age (AGA) status for infants at admission to the NICU will be based on Fenton’s Growth Curves. Humidity in the incubators to minimize insensible water loss will be used as per our thermoregulation protocol for preterm and VLBW infants.

Data Collection and Outcome Variables:

Data collection will be completed by research assistant employed in the NICU. After the infants are enrolled, the neonatal-perinatal fellow or research assistant will collect the following information: maternal and neonatal demographic data, birth weight, gestational age at birth, daily weight, serum triglyceride levels, and other nutritional laboratory values during the days on PN, dose of IVLE, fluid intake, maximum percentage of weight loss (defined as: (birth weight–lowest postnatal weight)/birth weight× 100), and day of regaining birth weight. To determine the day of regaining birth weight, the infant should have 2 consecutive readings above the birth weight, then the first day of the 2 readings will be considered the day of regaining birth weight. The study team will collect clinical outcomes such as necrotizing enterocolitis (NEC) (Stage II and above according to Bell staging), BPD, intraventricular hemorrhage (IVH), ROP, death and EUGR. Survival free major morbidity (BPD, severe ROP, NEC and severe IVH) at discharge will be collected and analyzed. Data on neurodevelopmental outcome by 18-22 months corrected gestation for baby less than 29 weeks will be collected from the neonatal follow-up clinic. BPD will be defined as being dependent on oxygen at postmenstrual age of 36 weeks. Intraventricular hemorrhage will be defined based on ultrasound scans obtained before day 15 of life according to the classification of Volpe and Levene. EUGR will be defined for our study

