as the presence of a measured weight below the 10th percentile at the time of hospital discharge on Fenton's growth Charts. Hyperglycemia will be defined as glucose level >10 mmol/L. Two registered dietitians will calculate fluids, calories and protein intakes and record the day of life when the infants achieved 100 and 120 ml/kg per day and age when PICC line is removed.

Sample Size and Statistical Analyses:

The primary statistical analysis will be to determine the effect of higher rates of parenteral fat intake on the maximum percentage of postnatal weight loss of the VLBW infants, during the first week of life. Independent, 2-sample, *t* tests will be used to compare the two groups for this primary outcome. Our previous data showed a maximum percent of weight loss in VLBW infants of: 11.4 (SD= 5.2). Drenckpohl et al. found that the weight loss in the first week was 8% only in the experimental group of VLBW infants who received higher dose of IVLE.²² We considered 8% a reasonable percentage of weight loss in this category of infants and calculated our sample size to decrease our percentage by 3.4% (from 11.4% to 8%). Assuming an α value of 0.05 and a power of 0.80, a sample size of 76 infants (38 in each group) will be required.

Continuous variables such as days to achieve 90 kcal/kg per day, biochemical laboratory results, amount of lipid infused, and anthropometric results will be analyzed using independent, 2-sample *t* tests. Categorical variables such as hypertriglyceridemia, proportions of EUGR infants, IVH, BPD and ROP will be evaluated using Pearson χ^2 tests. All statistical tests will be 2-tailed, and the level of significance will be set at 0.05. All statistical analyses will be performed using STATA 11.1 (College Station, TX).

Feasibility and safety:

There are currently about 225 infants born at less than 1500 grams at FMC every year. With a 30% enrollment rate, the sample size will be reached in around 18 months. Halfway through enrollment, the overall rate of lipid intolerance will be reviewed. This will allow for a check for any unexplained sudden increase in incidence of lipid intolerance in relation to the study, or a significant reduction that may allow decreasing of the number needed to enroll. Neonatology section research assistant and study coordinator will help in recruiting and collecting the data.

Plans for dissemination or translation of results and plans for next steps in study of topic:

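### The primary t test ignores same-arm siblings and omits birth weight, which is already collected; one prespecified model would handle both, and the stated 80% power holds only for independent infants

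*Combined protocol and SAP*

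**What the plan says.** - **Primary analysis** (Sample Size and Statistical Analyses): independent two-sample t "tests will be used to compare the two groups for this primary outcome". No covariate, regression model or allowance for siblings is described. The inputs are a mean of 11.4 (SD 5.2), a target of 8, two-sided alpha 0.05 and power 0.80, giving 76 infants (38 per group).
- **Outcome**: "The maximum percentage of weight loss in the acute stage of nutritional support", calculated as the fall from birth weight to the lowest postnatal weight, divided by birth weight.
- **Data collected** (Data Collection and Outcome Variables): "maternal and neonatal demographic data, birth weight, gestational age at birth, daily weight", among other items.
- **Randomization** (Study Protocol): "in random sized blocks for allocation concealment and balanced groups". No stratification factor is named.
- **Siblings** (Study Population): "Twins and triplets who meet the weight and AGA status criteria will be randomized to the same arm of the study".
- **Control schedule** (Study Protocol): the starting dose depends on birth weight, with "1 g/kg per day if birth weight is more than 1000g", and then "The IVLE dose in the control group will be increased by 0.5 g/kg per day daily until reaching 3 g/kg per day". The Appendix lists the daily doses and gives totals of 17, 10.5 and 12 g/kg, with a stated difference of 5 to 6.5 g/kg.

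**The concern.** Two features of the data are missing from the primary analysis.

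The first concerns validity. Siblings in the same arm share a mother, a gestation and a treatment. If their weight losses are positively correlated, 76 infants carry less information than 76 independent ones. The t test then reports an interval that is too narrow and rejects a true null hypothesis more often than 5% of the time.

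The second concerns efficiency. Birth weight is fixed before treatment and already recorded. If it predicts percentage weight loss, adjusting for it narrows the interval and corrects for chance imbalance, which blocking without stratification does not prevent. The trial is not blinded, so a decision to adjust that is taken after the data are seen would be a post hoc choice between two estimates.

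The plan has little slack: power is 0.803 for independent infants, and the sample-size paragraph states no dropout allowance.

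**Working it through.** **1. The plan's own figure.** Inputs from the sample-size paragraph: difference 3.4, SD 5.2, 38 per arm.

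- SE = 5.2 × √(2/38) = 1.193.
- 95% half-width = 1.9925 × 1.193 = 2.377 points (74 df).
- Noncentrality = 3.4/1.193 = 2.850, so noncentral-t power = 0.803. The 76 infants are reproduced, for independent infants.

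**2. Siblings and the planned test.** The documents give neither the share of multiples nor the within-pair correlation. Assume a share p of infants in twin pairs of 0.2 to 0.4, and a correlation ρ of 0.2 to 0.6. The variance of the arm difference is inflated by about 1 + pρ:

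- Mild end: 1 + 0.2 × 0.2 = 1.04.
- Strong end: 1 + 0.4 × 0.6 = 1.24.

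Type I error of the planned t test = P(|t₇₄| > 1.9925/√inflation):

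- 1.04: cut-off 1.954, error 0.054.
- 1.24: cut-off 1.789, error 0.078.

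Unadjusted power with the correct standard error (noncentrality 2.850/√inflation):

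- 1.04: 2.795, power 0.788.
- 1.24: 2.559, power 0.714.

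**3. Birth weight alone, independent infants.** R² is the share of within-arm outcome variance that birth weight explains. It is not in the documents; assume 0 to 0.15. Residual SD = 5.2 × √(1 − R²), with 73 df. The last column multiplies the variance by 73/72, the average cost of chance imbalance in the covariate.

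| R² | Power | Half-width | Power with 73/72 |
|---|---|---|---|
| 0 | 0.803 | 2.378 | 0.798 |
| 0.05 | 0.823 | 2.317 | 0.817 |
| 0.10 | 0.842 | 2.256 | 0.837 |
| 0.15 | 0.862 | 2.192 | 0.858 |

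At R² = 0.15 the gain equals 76/0.85 = 89.4 infants, about 13 more. Break-even on half-width is R² = 1 − (72/73) × (2.37703/2.37757)² = 0.014, a correlation of about 0.12. The worst case is a loss of about half a point (0.803 to 0.798).

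**4. Both together.** Simulation of the proposed model: 76 infants, twin pairs sharing an arm, assumed within-pair birth-weight correlation 0.7, cluster-robust standard errors, 6,000 runs per setting (Monte Carlo SE of power about 0.005). Each cell shows the result without, then with, birth weight.

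| Share in pairs, correlation | R² | Power | Half-width |
|---|---|---|---|
| 20%, 0.2 | 0 | 0.777 → 0.775 | 2.42 → 2.43 |
| 20%, 0.2 | 0.15 | 0.776 → 0.842 | 2.43 → 2.24 |
| 30%, 0.4 | 0.05 | 0.763 → 0.780 | 2.50 → 2.44 |
| 40%, 0.6 | 0 | 0.714 → 0.711 | 2.63 → 2.64 |
| 40%, 0.6 | 0.15 | 0.713 → 0.784 | 2.63 → 2.43 |

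Type I error was 0.054 for both robust models at 30%, 0.4 and R² 0.05. The formula in step 2, with the residual SD reduced for R² 0.15, gives 0.849 (mild) and 0.782 (strong), in line with the simulation.

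**5. Appendix, separately.** Sums over Days 0 to 5:

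- Experimental: 2 + 3 + 3 + 3 + 3 + 3 = 17 (printed 17).
- Control, 1000 g or less: 0.5 + 1 + 1.5 + 2 + 2.5 + 3 = 10.5 (printed 10.5).
- Control, above 1000 g: 1 + 1.5 + 2 + 2.5 + 3 + 3 = 13 (printed 12).

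The rows imply differences of 17 − 10.5 = 6.5 and 17 − 13 = 4 g/kg, against a printed lower limit of 5. At the Appendix's own 10 kcal/g that is about 40 to 65 kcal/kg, against 50 to 65. A different window does not explain it: Days 1 to 5 give 12 for this column, but 15 and 10 for the other two.

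**The case against.** **Adjustment is optional.** An unadjusted comparison is a legitimate primary analysis, the sample size follows from it, and the benefit starts at zero. This stands. The birth-weight part is an efficiency improvement and not the correction of an error.

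**R² may be small.** The outcome is already a percentage of birth weight, and enrolment is restricted to appropriately grown infants below 1500 g. This also stands, and it is why the range starts at zero. A reader might infer that birth weight must be prognostic from the Background statement "The proportion of weight loss is significantly higher in VLBW infants", or from the weight-dependent control schedule. Neither supports that: the statement contrasts these infants with term infants, and a dose rule does not show that the outcome varies with birth weight within this population.

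**Why not gestational age?** It is collected too, and would be defensible. Birth weight has the practical merit that the outcome cannot be computed without it, so it is never missing where the outcome exists. What matters is that the choice is fixed in advance.

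**The two issues differ in kind.** This is correct. Siblings bear on whether the test holds its level; birth weight bears on precision. They are taken together only because one model deals with both. The Appendix slip is unrelated and lends no weight to either.

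**Conclusion.** The point holds as a change that should be made, at medium confidence. Omitting birth weight leaves the t test unbiased, and the arithmetic behind 76 infants is sound for independent infants. It would still be too generous to call the planned test simply valid: with siblings in the same arm, its type I error is about 0.054 to 0.078 and correctly computed unadjusted power is about 0.79 to 0.71, under the assumed sibling range.

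Compared like for like with an unadjusted sibling-robust analysis, adding birth weight changes power by about 0 to +7 points and the half-width by about 0 to −0.20 points for R² of 0 to 0.15, with a worst-case loss of about half a point of power.

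A reader might infer that adjustment lifts power above the planned 0.80. The figures do not support that in general: the proposed model gives about 0.71 to 0.78 in the simulation at R² = 0, and 0.78 to 0.84 at R² = 0.15. A reader might also infer that the Appendix error undermines the sample size. It does not, because the calculation never uses that table. The mismatch of 1 g/kg is minor.

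**What to change.** 1. Prespecify the primary analysis as a linear model of maximum percentage weight loss on arm and continuous birth weight, with standard errors clustered on sibling set.
2. Keep the unadjusted difference, with the same clustered standard errors, as a sensitivity analysis. Any estimates by 1000 g band should be descriptive only.
3. State in the sample-size paragraph that 0.80 power assumes independent infants, and report the expected share of multiples with the power that follows.
4. Separately, reconcile the Appendix daily rows, the total for infants above 1000 g and the stated difference. Which entry was intended is for the investigators to say.

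The cost is a few sentences and an Appendix check, with no new data. Adding birth weight costs one degree of freedom and at most about half a point of power. Allowing for siblings lowers the power that can honestly be claimed, but the same-arm rule already causes that loss; the model only makes it visible. Adjustment will not necessarily restore 0.80.

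### Attained growth Z scores and EUGR are compared without using recorded size at birth: the tests are valid, but they give up precision on secondary outcomes that a baseline-adjusted model would recover at no cost

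*Combined protocol and SAP*

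**What the plan says.** The Outcome section lists, among the secondary outcomes, "Growth anthropometrics (weight, length and HC Z scores at 36 weeks and at discharge", and "Incidence of EUGR at 36 weeks and at discharge". Both are attained values. The Z scores are not defined as change from birth. Data Collection and Outcome Variables defines EUGR by weight under a fixed 10th-percentile line on the Fenton charts, whatever the infant's percentile at birth.

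Sample Size and Statistical Analyses says that "amount of lipid infused, and anthropometric results will be analyzed using independent, 2-sample" t tests, and assigns the proportion with EUGR to Pearson chi-square. The plan contains no covariate, regression model or change-from-birth analysis. Study Protocol describes randomisation in blocks of random size and states no stratification by size at birth.

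The baseline values will be on file. Birth weight and gestational age are in the data collection list, and Study Protocol says: "Other anthropometric measurements such as length and head circumference will be taken by nursing personnel on admission and then weekly till discharge".

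**The concern.** Where an infant ends up on the growth chart depends partly on where it started. The protocol's own argument says so. The Background cites a cohort in which infants seldom changed percentile once the early loss was over and then grew at similar rates, and it reasons that a smaller early loss should leave infants on a higher trajectory with less EUGR. On that reasoning, later Z is roughly birth Z less the early loss, so birth Z should be prognostic. The growth Z scores and EUGR are the outcomes that examine this argument.

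The primary outcome is expressed relative to each infant's birth weight, and so is time to regain birth weight. The attained Z scores and EUGR are not. Leaving birth size out adds avoidable noise to these comparisons. It also leaves the estimate exposed to whatever difference in birth size chance produces between two arms of 38.

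**Working it through.** **1. The plan's own figure.** The inputs, from Sample Size and Statistical Analyses, are a difference of 3.4 points (11.4% to 8%), SD 5.2, two-sided alpha 0.05 and power 0.80. The normal formula gives 2 × (5.2 × (1.960 + 0.842)/3.4)² = 36.7 per arm. The t-distribution version gives 37.7, so 38 per arm. This matches "a sample size of 76 infants (38 in each group) will be required". The calculation concerns the primary outcome only; the growth outcomes were not sized.

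**2. Chance imbalance in birth-weight Z.** Assumption: appropriate for gestational age means the 10th to 90th percentile, and birth-weight Z is normal within that band. With c = 1.2816, the variance is 1 − 2cφ(c)/0.80 = 0.438, so the SD is 0.662.

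- SE of the difference in arm means = 0.662 × √(2/38) = 0.152.
- 95% range = ±1.96 × 0.152 = ±0.30.
- A gap above 0.2 Z arises in about 19% of trials.

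If the SD were 1.0, which is possible for length and head circumference because the weight-based criterion need not restrict them, the SE is 0.229, the range is ±0.45, and a gap above 0.2 arises in about 38% of trials. These figures treat the infants as independent. Twins and triplets go to the same arm (Study Population), and some infants may die before assessment. Both would widen the range.

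**3. How much reaches the outcome.** The expected shift is the slope of later Z on birth Z times the birth-Z gap. A gap of 0.30 shifts the estimate by 0.30 at slope 1 and by 0.15 at slope 0.5. The documents give no slope.

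**4. Precision recovered, continuous Z scores only.** Adjustment multiplies residual variance by 1 − r², where r is the birth-to-outcome correlation (assumed). The last column further assumes an outcome SD of 1.0, where the unadjusted detectable difference at 80% power is (1.960 + 0.842) × √(2/38) = 0.64.

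| r | 1 − r² | SE multiplier | Equivalent n per arm (38/(1 − r²)) | Detectable difference |
|---|---|---|---|---|
| 0.3 | 0.91 | 0.95 | 41.8 | 0.61 |
| 0.5 | 0.75 | 0.87 | 50.7 | 0.56 |
| 0.7 | 0.51 | 0.71 | 74.5 | 0.46 |

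**5. Validity of the raw t test.** In simulated trials with no treatment effect, 38 independent infants per arm and slopes of 0.5, 0.8 and 1.0, its type I error was 0.049 to 0.051, and the mean estimated difference was essentially zero. Conditional on a birth imbalance of exactly 1.96 SE, the rejection probability follows from a normal variable with mean 1.96r and variance 1 − r². It is 0.08, 0.13 and 0.21 for r = 0.3, 0.5 and 0.7.

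**6. EUGR.** In the same simulations (later Z = −0.8 + slope × birth Z + noise of SD 0.6, all assumed, giving EUGR rates of 24% to 30%), a birth-Z gap of 0.2 moved the EUGR difference by about 5 to 8 percentage points. The 1 − r² factor is a linear-model result and does not carry over to this binary outcome.

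**The case against.** The strongest reply is that nothing here is invalid. Randomisation makes the raw comparison unbiased, and its standard error already includes chance differences in birth size. The same remark could be made about any prognostic factor in any unadjusted trial. That stands, and step 5 bears it out. A reader might infer that the planned growth comparisons are biased or have an inflated error rate; the documents do not support that. The raised rates in step 5 apply only to a trial that happens to be imbalanced.

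A reader might also infer that a birth-size difference passes through in full. It does so only at slope 1. The Background supports a substantial slope but gives no figure.

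Nor does the design ignore birth size. Eligibility is limited to infants appropriate for gestational age, and those born small are excluded. This narrows the spread of birth-weight Z but does not equalise the arms.

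The size of the gain is uncertain. The correlations and SDs are assumptions, and the upper end is demanding. With a birth SD of 0.66 and an outcome SD of 1.0, r = 0.7 needs a slope of 0.7/0.66 = 1.06, while a slope of 0.5 gives r = 0.33 and removes only about 11% of the variance (0.33² = 0.109). This also stands, and is why a range is given.

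Finally, these are secondary outcomes, the stated hypothesis concerns weight loss, and the Background presents the link to EUGR as speculation. That limits the importance of the point but does not remove it, because the covariates are already collected.

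**Conclusion.** The point holds as a minor improvement to the secondary analyses. The growth Z scores and EUGR are attained values tested without adjustment, although size at birth is recorded and the protocol's rationale makes it prognostic. The cost is lost precision, plus an estimate that moves with any chance birth-size imbalance in proportion to the slope.

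For birth-weight Z, 95% of chance differences lie within about ±0.30, given normality within the 10th to 90th percentiles, independent infants and 38 per arm. The range would be wider with multiples and deaths, and possibly wider for length and head circumference. For the continuous Z scores, adjustment would remove 9% to 49% of residual variance if the birth-to-outcome correlation is 0.3 to 0.7. No such gain is claimed for EUGR.

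A reader might take this as a challenge to the primary result or the sample size. It is neither: the primary outcome is already scaled to birth weight, and the 76 infants reproduce.

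**What to change.** In Sample Size and Statistical Analyses, replace the t test for each growth Z score, at 36 weeks and at discharge, with a linear model on arm plus the birth or admission Z score of the same measure. Use standard errors that allow for multiples allocated to the same arm, for example clustered by mother. Keep the raw comparison as supportive. Covariate adjustment is safer than a simple change score: with equal SDs, the change score's variance relative to the raw comparison is 2(1 − r), so it is more precise only when r exceeds 0.5.

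For EUGR, keep the planned comparison and add a supportive analysis adjusted for birth-weight Z, such as logistic regression reported as a marginal risk difference, again allowing for multiples. Reporting the odds ratio from that model instead would change the quantity estimated, because a conditional odds ratio differs from the unadjusted one.

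The cost is a few sentences, written before outcome data are examined so that the decision to adjust does not depend on an observed imbalance. No new data are needed, and the primary analysis and sample size stay as they are.

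### The halfway safety check reviews one overall lipid-intolerance rate, which cannot show whether a rise comes from the higher-lipid regimen; counts by arm would

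*Combined protocol and SAP*

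**What the plan says.** Feasibility and safety describes one look at trial level: "Halfway through enrollment, the overall rate of lipid intolerance will be reviewed". Its first purpose follows: "This will allow for a check for any unexplained sudden increase in incidence of lipid intolerance in relation to the study". A second purpose, "or a significant reduction that may allow decreasing of the number needed to enroll", is a separate matter and is not pursued here.

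Under Outcome, "intolerance will be defined as TG> 2.8 mmol/L". The target is 38 infants per group, and allocation is "in random sized blocks for allocation concealment and balanced groups". Under Study Design, "This is a randomized, non-blinded, controlled trial".

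The section attaches no split by arm, reference rate or threshold to this look. Hypertriglyceridaemia does appear among the variables for a Pearson chi-square test in Sample Size and Statistical Analyses, but that paragraph is not tied to the halfway review. Under Study Protocol, TG is measured 24 hours after each lipid increment as routine care, and Table 1 sets out what happens to an infant's lipid when TG is raised.

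**The concern.** The arms are meant to differ in how fast lipid is given. An excess of intolerance caused by the new regimen is therefore, first of all, a difference between arms. One overall figure hides that difference. A rise seen in it could come from the regimen, from a sicker intake affecting both arms, or from a change in how often TG is measured. A regimen effect could also sit inside a pooled rate that looks unremarkable.

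At stake is whether the only trial-level safety look can answer the question the plan sets for it. If it cannot, the team may blame the regimen for a unit-wide rise, or miss that the cases come from one arm.

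**Working it through.** **Inputs.** Total 76, 38 per group (Sample Size and Statistical Analyses). Intolerance is TG above 2.8 mmol/L (Outcome). Lipid schedule by day (Appendix). The documents give no intolerance rate, so every rate below is an assumption or an illustration.

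**The plan's own figure.** With a difference of 3.4, SD 5.2, two-sided alpha 0.05 and power 0.80, n per arm = 2 × (1.960 + 0.842)² × 5.2² / 3.4² = 36.7, so 37 by the normal approximation. The t-based calculation gives 37.7, so 38 per arm and 76 in total. The stated size reproduces.

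**Size at the look.** 76 / 2 = 38 infants, or about 19 per arm. This is approximate, because blocks may be incomplete and multiples share an arm.

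**Attribution.** Take 10 intolerant infants: 10/38 = 26%. The same figure arises from each of these splits:

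| Control | Higher lipid | Pooled | Fisher p, two-sided |
|---|---|---|---|
| 5/19 (26%) | 5/19 (26%) | 10/38 | 1.00 |
| 2/19 (11%) | 8/19 (42%) | 10/38 | 0.06 |
| 1/19 (5%) | 9/19 (47%) | 10/38 | 0.008 |
| 0/19 (0%) | 10/19 (53%) | 10/38 | 0.0004 |

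No baseline need be assumed for this. The pooled number does not change, while the evidence about the regimen runs from none to strong.

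**Dilution.** With equal arms, pooled rate = (control rate + higher-lipid rate) / 2. If controls stay at their usual rate, the pooled rise is half the excess: 20 points appears as 10, and 30 as 15.

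**Sensitivity.** Dilution alone does not settle this, since pooling also doubles the sample. The table gives the chance of a flag at 19 per arm. The pooled rule is a one-sided 5% exact rule for 38 infants against a baseline treated as known. The by-arm rule is a one-sided 5% z test of higher lipid against concurrent control.

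| Assumed baseline | Excess (points) | Pooled v known baseline | Arm v control |
|---|---|---|---|
| 5% | 20 | 0.70 | 0.57 |
| 10% | 20 | 0.50 | 0.47 |
| 10% | 30 | 0.79 | 0.72 |
| 20% | 20 | 0.34 | 0.40 |
| 30% | 20 | 0.33 | 0.36 |

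Neither rule is better throughout. A two-sided chi-square between arms has power of only 0.26 to 0.42 for a 20-point excess over baselines of 5% to 30%.

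**Unequal numbers of TG checks.** From the Appendix, the experimental arm has one increment (2 to 3 g/kg/day). Controls have five if 1000 g or less (0.5 to 3 in steps of 0.5) and four if above 1000 g (1 to 3). TG checks tied to increments thus give controls more chances to be found intolerant, on later days. A raw by-arm rate could mislead unless the same days are counted in both arms.

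**The case against.** **Each infant is already protected.** This stands. TG follows each increment and Table 1 applies in both arms. A reader might infer that infants on the higher regimen are unmonitored, and the documents do not support that. But Table 1 reacts to one infant's result; it does not tell the team whether the regimen produces more cases.

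**Pooling does not make the look clearly less sensitive.** This also stands. A reader might infer from the halving that the pooled check will miss an excess that a by-arm check would catch. The sensitivity table does not bear that out. Larger gains (for example 0.72 against 0.50 at baseline 10% and excess 20 points) come from testing the higher-lipid arm alone against a known baseline, which the documents do not print.

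**The unit may hold a prior rate.** This is fair. TG monitoring is routine there, and the plan uses the unit's earlier data for weight loss. An unprinted rate is not an unavailable one. Yet a pooled rise above a prior rate would still not show which arm it came from.

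**The control arm may also differ from past practice.** The Background describes current lipid starting at 12-24 hours of age, while Study Protocol starts controls after birth and the design calls their regimen traditional. These passages need to be reconciled. If control timing did change, a study-related rise need not be purely a difference between arms. That is a further reason to see each arm beside any prior rate.

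**The word *overall* is undefined, and an arm comparison exists elsewhere.** Nothing forbids a split, and a chi-square test of hypertriglyceridaemia is planned. One cannot say the arms will never be compared, only that the halfway look as written does not compare them.

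**Conclusion.** The point holds as one of attribution. As written, the halfway figure cannot show whether an increase is related to the regimen: 10/38 covers everything from 5 v 5 to 0 v 10. This rests on reading *overall* as pooled and on roughly equal arms at halfway; it does not depend on any assumed intolerance rate. Halving is exact only with equal arms and controls at their usual rate.

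It does not extend to a promise of better detection. At 19 per arm, estimates are wide: for 5/19 the exact (Clopper-Pearson) 95% interval runs from about 9% to 51%. Nor is it a failure of individual safety. It is a gap in trial-level monitoring, in an open-label trial where pooling protects no blind, and a cheap improvement.

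**What to change.** Replace the sentence on the halfway review with wording such as:

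> At the midpoint of enrolment, the number and proportion of infants with lipid intolerance (TG > 2.8 mmol/L), and the numbers whose lipid was reduced or stopped under Table 1, will be reviewed by randomised arm. The review will be descriptive, with confidence intervals, and will cover a common window of days in both arms, because TG is checked after each increment and the arms have different numbers of increments. The unit's prior rate will be shown alongside if available. Weight loss will not be tabulated by arm.

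The cost is a short rewrite, a choice of window, and a two-column table from TG and lipid-dose data already collected for each infant. With weight loss left out, the look spends no alpha on the primary outcome. The downside is that the team sees a by-arm safety rate during the trial, imprecise at about 19 per arm. The trial is already open label, so little is given away, but the intervals should be shown so that a chance imbalance is not over-read.
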